9.1.2. Secondary Assessments

Study IOQV will have 5 secondary efficacy measures as described in Table IOQV.2. The first secondary objective is similar to the primary objective (Section 9.1.1) except that the information to be analyzed will be using unblinded CGM data. Missed bolus doses will be determined by the glucose excursion as measured by the unblinded CGM.

Study IOQV will also estimate the percent time-in-range in subjects with T1D or T2D using blinded and unblinded CGM data. The glucose range for this analysis is >70 and ≤ 180 mg/dL. In addition, the percent of missed bolus doses per month and the average number of missed bolus doses per day will be estimated in subjects with T1D and T2D on both the blinded and unblinded CGM. The final secondary objective will estimate the average number of MSBD events per month in subjects with T1D or T2D using data obtained from the blinded and unblinded CGM phases of the study.

9.1.3. Exploratory Assessments

Study IOQV will possibly explore 6 different PRO evaluations that the subject will perform at time points outlined in the SOA ([Table IOQV.1](#)). These PRO evaluations are the Hypoglycemic Confidence Scale (HCS), Adult Low Blood Sugar Survey (ALBSS), the Big Five Inventory (BFI), Health Problem Solving Scale (HPSS), the Pictorial Representation of Illness and Self Measure Revised II (PRISM R II), and the General Life Stress Scale (GLSS). The details of each PRO evaluation are listed in the following sections.

9.1.3.1. Hypoglycemic Confidence Scale

The HCS examines the degree to which people with diabetes feel able, secure, and comfortable regarding their ability to stay safe from hypoglycemic-related problems (Polonsky et al. 2017). The HCS has been validated for use in adults with T1D and insulin-using T2D patients. This evaluation uses the Likert scale with ratings of not confident at all, a little confident, moderately confident, and very confident to rate a subject's response to 9 items during the evaluation (8 items for subjects without a partner and 9 for subjects with a partner). Each item will receive a score from 1 to 4 based on the subject's response. Scores are calculated as the sum total item score divided by the number of items completed (8 items for participants without a partner and 9 for participants with a partner). Higher scores mean greater confidence (Polonsky et al. 2017).

9.1.3.2. Adult Low Blood Sugar Survey

The ALBSS is an evaluation of the fear of hypoglycemia derived from the widely used and validated ALBSS. This evaluation uses the Likert scale of 0 ("never") to 4 ("almost always") to rate 11 items (Behavior domain with 5 items; Worry domain with 6 items). A higher total score means greater fear (Cox et al. 1987; Grabman et al. 2017).

9.1.3.3. The Big Five Inventory

The BFI is 44-item inventory that measures an individual on the Big Five Factors (dimensions) of personality, Extraversion versus introversion (8 items), Agreeableness versus antagonism (9 items), Conscientiousness versus lack of direction (9 items), Neuroticism versus emotional stability (8 items), and Openness versus closedness to experience (10 items). Identifying a patient's thinking, feeling, and behaving may help clinicians avoid suggesting solutions that will not work for that patient's personality type (APA WWW). The evaluation uses a Likert scale of (1) disagree strongly, (2) disagree a little, (3) neither agree nor disagree, (4) agree a little, and (5) agree strongly. (Goldberg 1981).

9.1.3.4. Health Problem Solving Scale

Patient problem-solving has been shown to be a predictor of coping and health behaviors and was related to improved outcomes in diabetes (Glasgow et al. 2007). The HPSS can be used to “identify patients who may be most in need of problem-solving interventions as part of patient education and disease self-management training” (Hill-Briggs et al. 2007). It is of interest to evaluate a person’s problem-solving abilities in association with the number of and/or frequency of missed mealtime insulin doses.

The scale is a set of 50 items that the subject rates using a 5-point Likert scale ranging from “not at all true of me” (0 points) to “extremely true of me” (4 points). Seven subscale scores are calculated by summing scores for each item in the respective subscale. The HPSS total score is derived by using the sums of the subscale averages, with reverse scoring of the negative subscales. Higher subscale scores indicate more of a problem-solving characteristic. A higher total HPSS score indicates a more effective health-related problem-solving skill (Hill-Briggs et al. 2007).

9.1.3.5. Pictorial Representation of Illness and Self Measure Revised II

The PRISM R II is a visual representation of burden of suffering from diabetes in a patient’s life. This evaluation allows for discussion on the importance of diabetes in the patient’s life that may provide insight into any barriers to successful diabetes management.

The PRISM R II consists of a large white paper circle, representing the subjects’ life, with a yellow paper circle placed in the middle and in front/on top of the white circle, representing the respondents’ self. Three differently sized red paper circles represent the respondents’ diabetes. The diabetes circles are respectively smaller than, equal to, and larger than the self circle. Subjects are given the following written instruction: “The white circle represents your current life and the yellow circle represents you. The three red circles represent your diabetes. Select from the three red circles the one that, in your view, represents your diabetes most accurately. Place the circle into your life. Locate the circle at the place that the diabetes occupies in your life. You can place the circle anywhere in your life, also entirely or partially on top of your self.” Two measures are extracted from the PRISM R II, Self Illness Separation where greater distances correspond to less burden and the Illness Perception Measure ranging from 1 to 3 with 1 representing the smallest disk (Klis et al. 2008).

9.1.3.6. General Life Stress Scale

The GLSS assesses the degree of stress an individual is currently experiencing in 5 general areas of life (finance, work, their romantic relationship, family, and health problems—modified to inquire about health problems other than diabetes) within 6 items, with response options ranging from 0 (“none”) to 4 (“a great deal”). The total score is calculated, with higher scores reflecting greater overall life stress (Hessler et al. 2016).

9.1.4. Appropriateness of Assessments

The objective collection of bolus dosing data using the pen will help to better understand actual dosing behavior. The use of the commercially available CGM device will provide an assessment

of blood glucose control to better understand the relationship with bolus dosing. The PROs will allow a better understanding of patient's behavior and the relationship with bolus dosing.

9.2. Adverse Events and Device Complaints

Investigators are responsible for monitoring the safety of subjects who have entered this study and for alerting Lilly or its designee to any event that seems unusual, even if this event may be considered an unanticipated benefit to the subject. The investigator is responsible for the appropriate medical care of subjects during the study. Investigators must document their review of each laboratory safety report.

The investigator remains responsible for following, through an appropriate health care option, AEs that are serious or otherwise medically important, considered related to the investigational product or the study, or that caused the subject to discontinue the investigational product before completing the study. The subject should be followed until the event resolves, stabilizes with appropriate diagnostic evaluation, or is reasonably explained. The frequency of follow-up evaluations of the AE is left to the discretion of the investigator. Lack of drug effect is not an AE in clinical studies.

Hypoglycemia, as outlined in Section 9.2.1.1, should be considered an AE when reported by the study participant.

After the informed consent form (ICF) is signed, study site personnel will record via the case report form (CRF) the occurrence and nature of each subject's preexisting conditions, including clinically significant signs and symptoms of the disease under treatment in the study. In addition, site personnel will record any change in the condition(s) and any new conditions as AEs. Investigators should record their assessment of the potential relatedness of each AE to protocol procedure, investigational device, or investigational product, via CRF.

The investigator will interpret and document whether or not an AE has a reasonable possibility of being related to study treatment, investigational study device, or a study procedure, taking into account the disease, concomitant treatment, or pathologies.

A "reasonable possibility" means that there is a cause and effect relationship between the investigational product, investigational study device and/or study procedure, and the AE.

The investigator answers yes/no when making this assessment. If relatedness to study device is "yes", a product complaint will also need to be submitted.

Planned surgeries and nonsurgical interventions should not be reported as AEs unless the underlying medical condition has worsened during the course of the study.

If a subject's investigational product is discontinued as a result of an AE, study site personnel must report this to Lilly or its designee via CRF, clarifying if possible, the circumstances leading to any dosage modifications, or discontinuations of treatment.

9.2.1. Serious Adverse Events

An SAE is any AE from this study that results in one of the following outcomes:

- death
- initial or prolonged subject hospitalization
- a life-threatening experience (i.e., immediate risk of dying)
- persistent or significant disability/incapacity
- congenital anomaly/birth defect
- important medical events that may not be immediately life threatening or result in death or hospitalization but may jeopardize the subject or may require intervention to prevent one of the other outcomes listed in the definition above. Examples of such medical events include allergic bronchospasm requiring intensive treatment in an emergency room or at home, blood dyscrasias or convulsions that do not result in subject hospitalization, or the development of drug dependency or drug abuse.
- when a condition related to the pen necessitates medical or surgical intervention to preclude either permanent impairment of a body function or permanent damage to a body structure, the serious outcome of “required intervention” will be assigned.
- severe hypoglycemia

All AEs occurring after signing the ICF are recorded in the CRF and assessed for serious criteria. The SAE reporting to the sponsor begins after the subject has signed the ICF and has received investigational product. However, if an SAE occurs after signing the ICF, but prior to receiving investigational product, the SAE should be reported to the sponsor as per SAE reporting requirements and timelines (see Section 9.2) if it is considered reasonably possibly related to study procedure.

Study site personnel must alert Lilly or its designee of any SAE within 24 hours of investigator awareness of the event via a sponsor-approved method. If alerts are issued via telephone, they are to be immediately followed with official notification on study-specific SAE forms. This 24-hour notification requirement refers to the initial SAE information and all follow-up SAE information. Subjects with a serious hepatic AE should have additional data collected using the CRF.

Pregnancy (during maternal or paternal exposure to investigational product) does not meet the definition of an AE. However, to fulfill regulatory requirements, any pregnancy should be reported following the SAE process to collect data on the outcome for both mother and fetus.

Investigators are not obligated to actively seek AEs or SAEs in subjects once they have discontinued and/or completed the study (the subject disposition CRF has been completed). However, if the investigator learns of any SAE, including a death, at any time after a subject has been discharged from the study, and he/she considers the event reasonably possibly related to the study treatment or study participation, the investigator must promptly notify Lilly.

9.2.1.1. Severe Hypoglycemia

Severe hypoglycemia is defined as an event accompanied by neuroglycopenic symptoms that result in cognitive impairment such that the patient requires assistance of another person to actively administer carbohydrate, glucagon, or perform other resuscitative actions. During these episodes, the patient has an altered mental status, and cannot assist in their care, is semiconscious or unconscious, or experienced coma with or without seizures, and may require parenteral therapy. Plasma glucose measurements may not be available during such an event, but neurological recovery attributable to the restoration of self-monitored blood glucose (SMBG) concentration to normal is considered sufficient evidence that the event was induced by a low SMBG concentration (≤ 70 mg/dL).

Documented symptomatic hypoglycemia is defined as an event that is accompanied by signs/symptoms of hypoglycemia, and is accompanied by a measured SMBG concentration of ≤ 70 mg/dL.

9.2.1.2. Suspected Unexpected Serious Adverse Reactions

Suspected unexpected serious adverse reactions (SUSARs) are serious events that are not listed in the USPI and that the investigator identifies as related to investigational product(s) or procedure. Lilly has procedures that will be followed for the identification, recording, and expedited reporting of SUSARs that are consistent with global regulations and the associated detailed guidances.

9.2.2. Adverse Device Effects

The investigator is responsible for sending to the sponsor within 24 hours any and/or associated product complaints involving a device malfunction of the pen, using the AE process and associated complaint report. Lilly will investigate all (S)AEs and associated complaints to determine the extent to which the event was caused by, or associated with, the investigational device.

Lilly will follow procedures consistent with US regulations to confirm and handle any unanticipated adverse device effects (UADEs), and will inform the Food and Drug Administration of confirmed UADEs following an investigation of the event. Within 10 working days of learning of the event, the principal investigator will then report evaluation results for any UADE to all reviewing Institutional Review Boards.

All UADEs will be summarized in the final study report.

9.2.3. Complaint Handling

Lilly collects product complaints on investigational products and drug delivery systems used in clinical studies in order to ensure the safety of study participants, monitor quality, and to facilitate process and product improvements.

Specifically, a product complaint is an expressed (written or verbal) statement regarding a deficiency in the expected performance of the device (e.g., did not work as intended; malfunctioned; difficult to use). A product complaint may occur independently from an AE, or along with an AE. A product complaint may also occur independently of a device malfunction.

The site is responsible for collecting all product complaints and reporting these to the sponsor via the provided product complaint form template. Device malfunctions on any Lilly product (e.g., failure of the investigational device to perform as intended) will be reported to the sponsor, irrespective of whether associated with an AE.

The investigator must instruct subjects to contact the clinical site as soon as possible if he or she has a complaint or problem with the product, investigational reusable insulin injection pen, or the commercially available CGM device so that the situation can be assessed.

All investigational reusable devices associated with complaints must be returned to the sponsor for evaluation.

9.3. Treatment of Overdose

Refer to product labeling for insulin lispro 100 units/mL (USPI).

9.4. Safety

9.4.1. Laboratory Tests

For each subject, the local laboratory test for HbA1c should be conducted according to the SOA (Table IOQV.1). A pregnancy test may be performed at the investigator's discretion if there is suspicion of possible pregnancy.

9.4.2. Safety Monitoring

Lilly will periodically review evolving aggregate safety data within the study by appropriate methods.

10. Statistical Considerations

10.1. Sample Size Determination

Approximately 68 subjects may be entered (i.e., signed informed consent) in order that 50 subjects complete the study. Subjects who are entered but not administered treatment may be replaced to ensure that enough subjects may complete the study. Assuming a screen fail rate of 15%, the expected number of subjects to be screened is 80. Up to 15 subjects may be enrolled at each investigator site.

A sample size of 50 completers (approximately 25 subjects with T1D and 25 subjects with T2D) is considered sufficient for this exploratory study.

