5.1.1. Eligibility and Enrollment

Subjects will be screened at Visit 1 (Week 0) for the assessment of enrollment eligibility. Screening assessments are outlined in the Schedule of Activities (SOA) ([Table IOQV.1](#)). Patients who pass screening assessments based on the inclusion and exclusion criteria set forth in Sections [6.1](#) and [6.2](#) are eligible to be enrolled in the study.

5.1.2. Study Period 1

At Visit 1 (Week 0), informed consent will be obtained from each subject.

Each subject will have a unique subject number assigned, additional eligibility requirements evaluated, and laboratory tests will be performed as outlined in the SOA ([Table IOQV.1](#)). After confirming eligibility (Visit 1), subjects will be trained on the devices to be used in the study. Subjects will be trained by the study site to self-insert the CGM sensor. If the subject cannot self-insert the CGM sensor, the site/study personnel will insert the CGM sensor. Subjects will be blinded to their CGM data. Subjects will continue their routine blood glucose monitoring as needed while using the blinded CGM device. However, subjects must monitor their blood glucose at least twice per day using a provided glucose monitor to calibrate the CGM device ([Section 7.1.2.1](#)).

Subjects will begin using the pen to inject insulin lispro 100 units/mL and the blinded CGM device as directed at Visit 1 (Week 0) after training. Subjects entering the study taking rapid-acting insulin analog other than insulin lispro 100 units/mL should be switched to insulin lispro 100 units/mL using a 1:1 dose conversion unless there are safety concerns as identified by the investigator. Subjects should continue their prestudy basal insulin and concomitant anti-hyperglycemic therapy and the investigator may adjust the insulin and other diabetes therapy as needed. In addition, the blinded CGM device will record the subject's glucose during Study Period 1 as outlined in the SOA.

A training checklist for the pen and the CGM device will be provided to investigators to aid in subject training. This training includes, but is not limited to, the operation of the pen and CGM device, CGM device calibration, clearing CGM alerts, and other study procedures. Subjects may be retrained on the aforementioned items if deemed appropriate by the study site. See [Section 7.1.2](#) for more information regarding the devices used in the study.

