5.2. Number of Subjects

Approximately 80 patients will be screened to achieve approximately 68 enrolled leading to approximately 50 evaluable subjects for Study IOQV. A minimum of 28 patients and a maximum of 40 patients each of T1D and T2D will be enrolled.

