6.4. Screen Failures

Individuals who do not meet the criteria for participation in this study (screen failure) may be rescreened.

7. Treatments

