10.3.1.1. Treatment Group Comparability

10.3.1.2. Subject Disposition

The primary reasons for discontinuation will be summarized by study period and subject allocation will be summarized by investigative site for the entered analysis set.

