Appendix 1. Abbreviations and Definitions

Term	Definition
AE	adverse event: Any untoward medical occurrence in a subject or clinical investigation subject administered a pharmaceutical product that does not necessarily have a causal relationship with this treatment. An AE can therefore be any unfavorable and unintended sign (including an abnormal laboratory finding), symptom, or disease temporally associated with the use of a medicinal (investigational) product, whether or not related to the medicinal (investigational) product.
ALBSS	Adult Low Blood Sugar Survey
BFI	The Big Five Inventory
CGM	continuous glucose monitoring
CIOMS	Council for International Organizations of Medical Sciences
complaint	A complaint is any written, electronic, or oral communication that alleges deficiencies related to the identity, quality, purity, durability, reliability, safety or effectiveness, or performance of a drug or drug delivery system.
compliance	Adherence to all study-related, good clinical practice (GCP), and applicable regulatory requirements.
CRF	case report form
CSR	clinical study report
enroll	The act of assigning a subject to a treatment. Subjects who are enrolled in the study are those who have been assigned to a treatment.
enter	Subjects entered into a study are those who sign the informed consent form directly or through their legally acceptable representatives.
ERB	ethical review board
FOIA	Freedom of Information Act
GCP	good clinical practice
GLSS	General Life Stress Scale
HbA1c	glycated hemoglobin
HCS	Hypoglycemic Confidence Scale
HPSS	Health Problem Solving Scale
IB	Investigator's Brochure

Term	Definition
ICF	informed consent form
ICH	International Council for Harmonisation
Informed consent	A process by which a subject voluntarily confirms his or her willingness to participate in a particular study, after having been informed of all aspects of the study that are relevant to the subject's decision to participate. Informed consent is documented by means of a written, signed and dated informed consent form.
investigational product	A pharmaceutical form of an active ingredient or placebo being tested or used as a reference in a clinical trial, including products already on the market when used or assembled (formulated or packaged) in a way different from the authorized form, or marketed products used for an unauthorized indication, or marketed products used to gain further information about the authorized form.
IOQV	F3Z-MC-IOQV

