8.1 Subject Disposition

The number and percentage of subjects who were screened, signed informed consent, completed, and discontinued, including discontinuation period, will be summarized. The number and percentage of subjects who discontinued will also be summarized for each reason for discontinuation. The summary will be made overall and by study site.

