12. TABLE SHELLS

The following table shells are provided in order to provide a framework of the statistical analysis for the study. These shells may not be reflective of every aspect of the analyses, but are intended to show the general layout of the tables that will be included in the final report.

Eli Lilly and Company
Protocol No. F3Z-MC-IOQV(a)

Table 14.1.1 - Disposition of Subjects

		Study Sites				Overall
		xxx	xxx	xxx	xxx	
Screened		xx	xx	xx	xx	xx
Signed Informed Consent		xx (xx.x%)	xx (xx.x%)	xx (xx.x%)	xx (xx.x%)	xx (xx.x%)
Completed	N	xx	xx	xx	xx	xx
	YES	xx (xx.x%)	xx (xx.x%)	xx (xx.x%)	xx (xx.x%)	xx (xx.x%)
	NO	xx (xx.x%)	xx (xx.x%)	xx (xx.x%)	xx (xx.x%)	xx (xx.x%)
Discontinuation in	Period 1 (Blinded CGM)	xx (xx.x%)	xx (xx.x%)	xx (xx.x%)	xx (xx.x%)	xx (xx.x%)
	Period 2 (Unblinded CGM)	xx (xx.x%)	xx (xx.x%)	xx (xx.x%)	xx (xx.x%)	xx (xx.x%)
Primary Reason for Discontinuation	N	x	x	x	x	x
	Adverse Event	x (xx.x%)	x (xx.x%)	x (xx.x%)	x (xx.x%)	x (xx.x%)
	Protocol Violation	x (xx.x%)	x (xx.x%)	x (xx.x%)	x (xx.x%)	x (xx.x%)
	Withdrawal by Subject	x (xx.x%)	x (xx.x%)	x (xx.x%)	x (xx.x%)	x (xx.x%)
	Physician Decision	x (xx.x%)	x (xx.x%)	x (xx.x%)	x (xx.x%)	x (xx.x%)
	Sponsor Decision	x (xx.x%)	x (xx.x%)	x (xx.x%)	x (xx.x%)	x (xx.x%)
	Lack of Efficacy	x (xx.x%)	x (xx.x%)	x (xx.x%)	x (xx.x%)	x (xx.x%)
	Lost to Follow-Up	x (xx.x%)	x (xx.x%)	x (xx.x%)	x (xx.x%)	x (xx.x%)
	Other	x (xx.x%)	x (xx.x%)	x (xx.x%)	x (xx.x%)	x (xx.x%)

Program: 14.1.1.xxxx.sas

Eli Lilly and Company
Protocol No. F3Z-MC-IOQV(a)

Table 14.2.1 - Missed Bolus Dose (Evaluable Population)

Parameter	Statistics	Insulin Injection	
		Period 1 (Blinded CGM) N = xx	Period 2 (Unblinded CGM) N = xx
Number of Days per Month with MBD	N	xx	xx
	Mean	xx.x	xx.x
	SD	xx.x	xx.x
	Median	xx.x	xx.x
	Minimum	xx.x	xx.x
	Maximum	xx.x	xx.x
Percent of Missed Bolus Doses	N	xx	xx
	Mean	xx.x	xx.x
	SD	xx.x	xx.x
	Median	xx.x	xx.x
	Minimum	xx.x	xx.x
	Maximum	xx.x	xx.x
Number of Missed Bolus Doses per Day	N	xx	xx
	Mean	xx.x	xx.x
	SD	xx.x	xx.x
	Median	xx.x	xx.x
	Minimum	xx.x	xx.x
	Maximum	xx.x	xx.x

Program: 14.2.1.xxxx.sas

Eli Lilly and Company
Protocol No. F3Z-MC-IOQV(a)

Table 14.3.1.1 - Number of Subjects with Adverse Events (Safety Population)

	Insulin Injection	
	Period 1 (Blinded CGM) N = xx	Period 2 (Unblinded CGM) N = xx
With At Least One Adverse Event	xx (xx.x%)	xx (xx.x%)
With At Least One Mild or Moderate Adverse Event	xx (xx.x%)	xx (xx.x%)
With At Least One Severe Adverse Event	xx (xx.x%)	xx (xx.x%)

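### Does calling the 68 planned subjects entered rather than enrolled leave the completion rate without a base?

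*Protocol*

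**What the plan says.** **Sample size.** Protocol 10.1, repeated in SAP 4.1, states: "Approximately 68 subjects may be entered (i.e., signed informed consent) in order that 50 subjects complete the study". Both then assume 15% screen failure and 80 screened. Protocol 5.2 gives the same chain under another label: "Approximately 80 patients will be screened to achieve approximately 68 enrolled leading to approximately 50 evaluable subjects for Study IOQV". The synopsis also lists the 68 as enrolled.

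**Definitions.** Appendix 1 of the protocol defines entering as signing consent, and on enrolment says: "Subjects who are enrolled in the study are those who have been assigned to a treatment".

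**Order of events.** Protocol Appendix 2.1.1 requires consent before any protocol procedure. Protocol 5.1.2 takes consent at Visit 1 and continues: "Each subject will have a unique subject number assigned, additional eligibility requirements evaluated, and laboratory tests will be performed". Devices are started at that visit once eligibility is confirmed. Protocol 6.4 adds: "Individuals who do not meet the criteria for participation in this study (screen failure) may be rescreened".

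**Disposition.** Protocol 10.3.1.2 says: "The primary reasons for discontinuation will be summarized by study period and subject allocation will be summarized by investigative site for the entered analysis set". SAP 8.1 says: "The number and percentage of subjects who were screened, signed informed consent, completed, and discontinued, including discontinuation period, will be summarized". The SAP table list (11.1) gives the population of Table 14.1.1 as Screened. The shell for that table runs from screened to consented to completed (with an N, yes and no), then to period of discontinuation and "Primary Reason for Discontinuation". It has no enrolled row and no screen-failure row.

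**Baseline and analysis sets.** SAP 8 plans baseline summaries on both the entered and the evaluable sets, with paired tables. Protocol 10.2 builds the evaluable and safety sets from enrolled subjects; SAP 5.2 and 5.3 build them from entered subjects. Both documents require at least 2 weeks of unblinded CGM for the first set and any CGM or pen use for the second.

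**The concern.** One number has two labels that the protocol itself defines differently, and the wrong one sits in the sample-size section. The planned disposition table then offers no enrolled count that would put it right, and the protocol and the SAP name different populations for that table.

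This seems to matter because the primary estimate, from the blinded period, is made only in subjects who later had at least 2 weeks of unblinded CGM. A reader who wants to judge that selection needs to know how many enrolled subjects were lost on the way. If people who failed screening after signing consent are counted among the non-completers, the loss looks larger than it was, and part of it concerns people who never received a device. The same people could also appear in the entered-set baseline tables. A rescreened person might be counted twice.

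**Working it through.** **Inputs.** 80 screened, 15% screen failure, 68, and 50 completers (Protocol 10.1, SAP 4.1, synopsis); 28 to 40 subjects enrolled per diabetes type (Protocol 5.2).

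**1. The plan's own figure.** Number screened = 68/(1 − 0.15) = 68/0.85 = 80. It reproduces exactly, and 80 − 68 = 12 screen failures.

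**2. Which label fits.** The division in step 1 works only if 68 is the count after screen failure. Suppose instead that 68 people signed consent and 15% of them then failed:

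- enrolled = 68 × 0.85 = 57.8
- completers at the planned retention = 57.8 × 50/68 = 42.5, not 50
- retention needed to reach 50 = 50/57.8 = 86.5%, against the planned 50/68 = 73.5%

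The limits per diabetes type agree with the first reading: one type at its minimum and the other at its maximum gives 28 + 40 = 68 enrolled. So 68 is the enrolled number, and the wording in Protocol 10.1 and SAP 4.1 is the slip.

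**3. Completion rate by base.** The number entered depends on how many of the 12 screen failures come after consent.

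| Failures after consent | Entered | Completion | Non-completers | Of whom screen failures |
|---|---|---|---|---|
| 0 | 68 | 50/68 = 73.5% | 18 | 0 |
| 6 | 74 | 50/74 = 67.6% | 24 | 6 (25%) |
| 12 | 80 | 50/80 = 62.5% | 30 | 12 (40%) |

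The widest gap is 73.5 − 62.5 = 11.0 points. The documents do not support all rows equally. Since consent precedes every protocol procedure, anyone who fails a protocol screening test has already entered, so the first two rows need failures before consent that no section describes. The last row is an upper bound, because it assumes that all 80 sign. The uncertainty about who belongs to the entered set is therefore smaller than the table suggests. What is left is whether entered or enrolled is the base for the percentages.

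**4. Reach into the results.** The safety set needs CGM or pen use and the evaluable set needs 2 weeks of unblinded CGM. Devices start after eligibility is confirmed, so a screen failure belongs to neither set, whether the definition opens with enrolled (Protocol 10.2) or entered (SAP 5.2 and 5.3). The change in every efficacy and safety estimate is 0. In the entered-set baseline tables, screen failures could be at most 12/80 = 15% of subjects, and the evaluable-set tables beside them contain none.

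**5. Can the loss to evaluable be seen?** The safety tables print an N for device users and Table 14.2.1 prints the evaluable N. Their difference closely approximates the loss that bears on selection, without screen failures. Listings 16.2.2 and 16.2.3 identify the individuals. Completion is in any case not the same measure: a subject who leaves late in Period 2 is evaluable without having completed.

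**The case for a change.** The best argument for a change is that the error is certain and cheap to correct. Protocol 10.1 itself recognises subjects who entered but were not treated, so the two words cannot be treated as synonyms. The SAP says its shells need not show every aspect of the analyses, but that does not cover the text of SAP 8.1, which also omits an enrolled count. Protocol 10.3.1.2 and the SAP table list disagree on the population. The schedule of activities places Visit 1 inside Study Period 1, so a failure after consent could be tabulated as a Period 1 discontinuation. No rule says that a rescreened person is counted once.

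Most of this stands as a description of the text. The mislabelling is real, the denominator is unstated and the counting rule is absent. The consequences are weaker. Nothing says that a screen failure is to be coded as a discontinuation, and the protocol keeps the two apart (6.4 against section 8). Baseline does not rest on the entered set alone. The selection created by the evaluable definition is a separate matter, which relabelling the 68 would not alter. A new enrolled analysis set, with the entered-set baseline tables dropped, would be more than the slip calls for.

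**Conclusion.** No change to the plan follows. The wording in Protocol 10.1 and SAP 4.1 is a clerical slip: the figures 80, 68 and 50 are right, and the synopsis and Protocol 5.2 label the 68 correctly. The possible effect is at most 11.0 percentage points (73.5% against 62.5%) on one descriptive disposition percentage, and that upper limit assumes that all 80 screened people sign consent. The effect on the primary, secondary and safety estimates is nil, provided that no one receives a device before eligibility is confirmed, as Protocol 5.1.2 lays down. The study is exploratory and descriptive, and no endpoint, sample-size re-estimate or decision uses the completion rate.

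Analysts can fill the open points from data the plan already collects. Enrolment is recorded at Visit 1, unmet eligibility criteria are listed, and the N printed in the disposition table shows the base in use. Reporting completion among enrolled subjects, showing screen failures apart and counting each person once is what a competent team would do without an instruction.
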